- Clinical safety data from AE reporting, 12-lead ECG, vital signs (supine blood pressure, heart rate, oral temperature), clinical laboratory evaluations (chemistry, haematology, urinalysis, and coagulation) and physical examinations in healthy male subjects.

Study Design:

This is a 2-part, randomised study.

Part A

Part A is a randomised, double-blind, crossover group study to investigate the safety, tolerability, and PK profile of a single oral dose of KLS-GABA compared to KLS alone in healthy male subjects. It is planned to enrol 12 subjects. All subjects will take part in 2 treatment periods, in which they will be randomised to receive either a single dose of KLS-GABA (80 mg-34 mg) or a single dose of KLS (80 mg) alone in each treatment period.

Subjects' participation in Part A will last approximately 7 weeks and will consist of the following:

- A screening visit (up to 28 days prior to Day 1 of Treatment Period 1),
- Admission to the clinical research unit (CRU) on Day -1 prior to Treatment Period 1,
- Treatment Period 1 (Day 1 to Day 3),
- A washout period of a minimum of 7 days,
- Admission to the CRU on Day -1 prior to Treatment Period 2,
- Treatment Period 2 (Day 1 to Day 3),
- A follow-up visit (5 to 7 days post-final dose following Treatment Period 2).

Safety will be assessed through AE reporting, 12-lead ECGs, vital signs, physical examinations, and clinical laboratory examinations. Pharmacokinetics will be assessed by blood sampling.

Part B

Part B is a randomised, double-blind, placebo-controlled parallel group study to investigate the PD effects, PK/PD correlation, safety, and tolerability of three single oral dose levels of KLS-GABA compared to KLS alone, 300 mg gabapentin and placebo in the ID capsaicin model in healthy male subjects.

It is planned to enrol 128 subjects, randomised evenly to 8 possible treatments; subjects will receive either KLS alone, KLS-GABA, 300 mg gabapentin or placebo. The planned treatments are:

- KLS alone (40 mg, 80 mg, or 160 mg)
- KLS-GABA (40 mg-17 mg, 80 mg-34 mg or 160 mg-68 mg)
- Gabapentin (300 mg)
- Placebo

Subjects' participation in Part B will last approximately 6 weeks and will consist of the following:

- A screening visit (up to 28 days prior to dosing),
- An additional screening visit (at least 7 days prior to dosing) to determine the subject's response to capsaicin and to familiarise them in the pain measurements,

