2.2. Objectives (Part B)

2.2.1. Primary Objective

The primary objective of the study is:

- To determine the pharmacodynamic (PD) effects of KLS-GABA in the ID capsaicin model in healthy male subjects.

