3. STUDY DESIGN

This is a Phase I, randomised, 2-part study to determine the PK, safety, and tolerability of single oral doses of KLS-GABA compared to KLS alone in healthy male subjects (Part A), in addition to investigating the PD effects, PK/PD correlation, safety, and tolerability of three single oral dose levels of KLS-GABA compared to three single oral dose levels of KLS alone, 300 mg gabapentin alone and placebo in the ID capsaicin model in healthy male subjects (Part B).

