3.4. Dose Rationale

Ketoprofen and gabapentin, the two individual components of the IMP, are both authorised medicinal products and have been widely used in clinical practice for many years. Therefore, the doses selected for this study are supported by clinical safety data deriving from extensive experience with these drugs.

The labelled doses of KLS are 40 mg up to 3 times per day, or KLS 80 mg up to 2 times per day. The maximum dose of ketoprofen is 200 mg. Gabapentin administration can be administered by titrating the dose (e.g., Day 1: 300 mg once a day; Day 2: 300 mg two times a day; Day 3: 300 mg three times a day), or by administering 300 mg three times per day from

Day 1. Based on individual patient response and tolerability, the gabapentin dose level can be further increased in 300 mg/day increments every 2 to 3 days, up to a maximum of 3600 mg/day.

The current study in healthy volunteers is planned to consist of a single oral dose of KLS-GABA (80 mg-34 mg) in Part A, and three oral dose levels of KLS-GABA once daily in Part B, as follows:

- KLS 40 mg/GABA 17 mg,
- KLS 80 mg/GABA 34 mg
- KLS 160 mg/GABA 68 mg

These doses are within the range considered to be safe and with acceptable tolerability in the previous clinical trials investigating both ketoprofen and gabapentin. Further details can be found in the IB or the SmPC.

The selection of dose and dose regimen specifically related to the KLS-GABA co-crystal is based on the currently available non-clinical information. In preclinical models, the co-crystal was proven to be more effective compared to administration of KLS alone, gabapentin alone and coadministration of KLS and gabapentin.

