10.5.4. Pharmacodynamic Statistical Analysis

Summaries and descriptive statistics will be produced for each PD parameter. This includes Scores (VAS or NRS) / Area measured (cm^2) for each treatment and timepoint, along with change from baseline in Score / Area.

Mixed Model Repeated Measures (MMRM) will be fit to data for each PD parameter using two groups of models. Group 1 will assess longitudinal changes in Scores / Area against baseline. Group 2 will assess differences in Scores / Area between treatments for each timepoint.

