2. STUDY DESIGN

This is a Phase I, randomised, 2-part study to determine the PK, safety, and tolerability of single oral doses of KLS-GABA compared to KLS alone in healthy male subjects (Part A), in addition to investigating the PD effects, PK/PD correlation, safety, and tolerability of three single oral dose levels of KLS GABA compared to three single oral dose levels of KLS alone, 300 mg gabapentin alone and placebo in the ID capsaicin model in healthy male subjects (Part B).

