2.2. Part B

Part B is a randomised, double-blind, placebo-controlled parallel group study to investigate single oral doses of KLS alone or KLS-GABA compared to 300 mg gabapentin alone or placebo, in healthy male subjects using the ID capsaicin model.

It is planned to enrol 128 subjects randomised evenly to 8 possible treatments; subjects will receive either KLS alone, KLS-GABA, 300 mg gabapentin or placebo.

The planned treatments are:

- KLS alone (40 mg, 80 mg or 160 mg)
- KLS-GABA (40 mg-17mg, 80 mg-34 mg, or 160 mg-68 mg)
- Gabapentin* (300 mg)
- Placebo

* Product commercialised in the UK: Neurontin 300 mg hard capsules.

Subjects will be required to attend the CRU for a screening visit within 28 days prior to dosing to ensure they meet the inclusion/exclusion criteria and are in good general health.

Statistical Analysis Plan

Following initial screening, subjects will be required to attend the CRU for an additional screening visit at least 7 days prior to first dosing to assess their response to capsaicin and familiarise them in the pain measurements. Subjects will receive a single ID administration of 100 µg capsaicin into a novel site on the volar surface of the forearm. Prior to and 15 minutes after administration of capsaicin, measurements of pain, hyperalgesia, allodynia and AF will be performed according to the procedures described in Section 9. In order for the subjects to be eligible, they must be able to tolerate the injection and also demonstrate a sufficient response, defined as an area of hyperalgesia $\geq 15\text{cm}^2$ 15 minutes after the injection.

Subjects will be admitted to the CRU on Day -1 for collection of baseline safety assessments, pain measurements and to complete the ID capsaicin model (see Appendix 2). Subjects will receive a single 100 µg capsaicin injection into a novel site on the volar surface of the forearm.

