6.8.3. PD Modelling

Two separate sets models will be fit to the data. Individual models will be fit per treatment group ("KLS 40 mg", "KLS 80 mg", "KLS 160 mg", "KLS 40 mg - GABA 17 mg", "KLS 80 mg - GABA 34 mg", "KLS 160 mg – GABA 68 mg", "Gabapentin 300 mg", "Placebo") to assess means and change from baseline in score and area for each PD parameter (see [Section 6.8.1](#)). Combined models will be fit using combined treatments (i.e. different doses of the same treatment combined – "KLS alone", "KLS-GABA", "Gabapentin", "Placebo") to assess differences in means and change from baseline in score and area for each PD parameter (see [Section 6.8.1](#)).

Individual models (by treatment):

The MMRM model will contain terms for the actual treatment group (and timepoint and will contain baseline Score / Area as a covariate and subject as a random effect.

An unstructured covariance matrix will be assumed. If the fit of the unstructured covariance structure fails to converge, the following covariance structures will be tried in order until convergence is reached: toeplitz with heterogeneity, autoregressive with heterogeneity, toeplitz, and autoregressive.

Least squares (LS) means will be reported by timepoint along with corresponding 95% confidence intervals (CIs).

The model will be fit separately for each treatment group, for the following dependent variables:

- Score / Area for each PD parameter
- Change in score / Area for each PD parameter

Combined models (treatment as a term; comparing against placebo):

The MMRM model will contain terms for actual combined treatment group and timepoint and will contain baseline Score / Area as a covariate and subject as a random effect.

An unstructured covariance matrix will be assumed. If the fit of the unstructured covariance structure fails to converge, the following covariance structures will be tried in order until convergence is reached: toeplitz with heterogeneity, autoregressive with heterogeneity, toeplitz, and autoregressive.

LS means will be reported by timepoint for each treatment group; the difference in LS means between each dose arm and placebo will be presented along with corresponding 95% CIs.

The modelling will be conducted separately for the following dependent variables:

Statistical Analysis Plan

- Score / Area for each PD parameter
- Change in score / Area for each PD parameter

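### The SAP pools Part B doses into four groups, so six of the seven dose-arm differences from placebo that it promises have no source model, and the pooling is not listed as a change

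*SAP*

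**What the plan says.** **Models.** Protocol 10.5.4.2 (Model Group 2) fits one repeated-measures model to all treatment groups, with randomised treatment as the term, and reports each dose arm minus placebo with 95% CIs. SAP 6.8.3 replaces this with a combined model whose treatment term has four levels, made by merging the doses of each product: KLS alone, KLS-GABA, gabapentin, placebo. It keeps the output sentence: "the difference in LS means between each dose arm and placebo will be presented along with corresponding 95% CIs".

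SAP 6.8.3 also has individual models. The text gives them a term for actual treatment, and then says they are fitted arm by arm. Their stated output is LS means with CIs; no differences are mentioned.

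SAP section 8 lists one change from the protocol, the Part B primary endpoint. The dose pooling is not there.

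**Comparison.** The protocol synopsis describes Part B as studying "three single oral dose levels of KLS-GABA compared to KLS alone, 300 mg gabapentin and placebo in the ID capsaicin model". Protocol section 3 says "three single oral dose levels of KLS-GABA compared to three single oral dose levels of KLS alone, 300 mg gabapentin alone and placebo", and SAP section 2 says the same. SAP 2.2 differs: "single oral doses of KLS alone or KLS-GABA compared to 300 mg gabapentin alone or placebo". The primary objective is "To determine the pharmacodynamic (PD) effects of KLS-GABA in the ID capsaicin model in healthy male subjects", with no comparator. Protocol 10.5.4 says "Group 2 will assess differences in Scores / Area between treatments for each timepoint", but both modelling sections then specify differences against placebo only.

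SAP section 3 rules out hypothesis testing, so the intervals are the main inferential output.

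**The concern.** A programmer following SAP 6.8.3 cannot produce the promised output from the model described. Someone would have to decide whether a dose arm means one of the eight randomised arms or one of the four pooled groups. On the second reading, the dose-level differences planned in the protocol disappear without being recorded.

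This affects what is learned. KLS-GABA and KLS are each given at three doses, and pooling averages over them. An effect confined to one dose would be diluted in the pooled estimate, and any dose trend against placebo would carry no model-based interval.

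The second, lesser matter is the active comparison. Three KLS-GABA doses are matched on KLS content to three KLS doses, which takes 96 of the 128 subjects. Protocol 3.4 records that in preclinical models "the co-crystal was proven to be more effective compared to administration of KLS alone, gabapentin alone and coadministration of KLS and gabapentin". A reader of the results will want KLS-GABA minus KLS with an interval, and the plan specifies none.

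**Working it through.** **1. Allocation (protocol 3.2 and 10.1; SAP 2.2).** 128 subjects are spread evenly over 8 arms: 128/8 = 16 per arm. Block size 16 gives 128/16 = 8 blocks, as the protocol states. Pooled group sizes are 48 (KLS-GABA), 48 (KLS), 16 (gabapentin) and 16 (placebo). There is no power calculation, effect size or SD to reproduce.

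**2. What each model can give.**

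| Model | Treatment levels | Differences from placebo | At arm level |
|---|---|---|---|
| Protocol Model Group 2 | 8 | 7 | 7 |
| SAP combined | 4 | 3 | 1 (gabapentin) |
| SAP individual, fitted arm by arm | 1 per fit | none within a fit | none |

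So 7 − 1 = 6 promised differences lack a source. If the individual models were instead one model with a treatment term, the differences could be estimated from it, but the stated output is still LS means only.

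**3. Effect of pooling.** With equal arms, the pooled mean weights the three doses equally. If only one dose had an effect d against placebo, the pooled difference would be (d + 0 + 0)/3 = d/3.

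**4. By-timepoint differences.** The SAP lists treatment and timepoint but no treatment-by-timepoint term. With main effects only, the fitted treatment difference is the same at every timepoint, so differences by timepoint need the interaction.

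**5. Precision.** Half-width = t(0.975) × √(1/n₁ + 1/n₂), in residual-SD units. Assumptions: common SD, one timepoint, no dropout. Degrees of freedom are 128 − 4 − 1 = 123 (t = 1.979) for four groups plus one covariate, and 128 − 8 − 1 = 119 (t = 1.980) for eight arms plus one covariate.

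- Pooled KLS-GABA minus KLS: √(2/48) = 0.204; × 1.979 = 0.40
- Pooled KLS-GABA minus gabapentin or placebo: √(1/48 + 1/16) = 0.289; × 1.979 = 0.57
- Any single arm minus another: √(2/16) = 0.354; × 1.980 = 0.70

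In outcome-SD units these are multiplied by √(1 − ρ²), where ρ is the correlation with baseline (not given). For an assumed ρ of 0.3 to 0.7 they become 0.39–0.29, 0.55–0.41 and 0.67–0.50. With an assumed 10% loss, the residual-SD values rise to 0.43, 0.60 and 0.74.

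**6. Score or change.** Both are planned as dependent variables with baseline as covariate. Since change = score − baseline, moving from one to the other alters the baseline slope by 1 and leaves treatment differences alone. A simulated check (128 subjects, 8 arms, 5 timepoints, timepoint-matched baseline) gave agreement to 1e-15 for all 35 arm-by-timepoint differences (7 × 5). One of the two is enough for added contrasts.

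**The case against.** The strongest objections concern the active comparison.

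- **A reader might infer that the plan breaks a commitment to compare KLS-GABA with KLS.** The documents do not support that. No primary or secondary Part B objective names a PD comparator, and placebo differences can answer the primary objective as worded. The study title uses comparison with KLS alone for Part A and calls Part B placebo-controlled. Protocol 3.2 and SAP 2.2 set both products against gabapentin or placebo. Protocol 10.5.4.2 itself narrows the differences to placebo, and the SAP follows it there. The study rationale (protocol 1.2) frames proof of concept as attenuating capsaicin effects, and protocol 3.4 rests the doses first on clinical experience with the components. This objection stands and limits the second part to a recommended addition.

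- **A reader might infer that the active comparison is lost, or would be defined only after unblinding.** Neither follows. SAP section 3 with 6.8.1 gives n, mean and SD by arm and timepoint, and 6.8.2 gives mean and SE figures, so approximate unadjusted comparisons are possible. Under the assumptions in step 5, the pooled KLS-GABA minus KLS half-width is the planned pooled placebo one times √(2/48)/√(1/48 + 1/16) = 0.707, that is 0.57 to 0.40. The protocol requires the SAP before database lock, and the table shells (SAP section 9) are a separate document, not seen, that may define contrasts.

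- **A reader might infer that the pooled model gives no arm-level difference.** It gives one, gabapentin minus placebo.

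None of this removes the mismatch between a four-level term and a promise for each dose arm, the conflicting text on the individual models, or the omission from section 8.

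**Conclusion.** The inconsistency is established from the text and needs no assumption about the data: SAP 6.8.3 promises seven arm-level differences from placebo and specifies a model that yields one of them. If the sentence was meant for pooled groups, the protocol's dose-level differences have been dropped without entry in section 8. This should be corrected.

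The missing intervals against KLS alone and gabapentin are a gap relative to how the design is described, not relative to the objectives. They are worth adding because the pooled KLS-GABA minus KLS contrast would be the most precise between-product estimate in the study (0.40 residual SD, against 0.57 for the planned pooled placebo difference). Single-arm contrasts, at 0.70, will be imprecise. These sizes rest on equal arms, a common SD, a single timepoint and no dropout; the SD itself is not in the documents.

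**What to change.** In SAP 6.8.3:

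1. Add an eight-arm model with actual treatment, timepoint, treatment-by-timepoint and baseline, and report each of the seven active arms minus placebo with 95% CIs by timepoint. Actual treatment matches the PD Set in SAP 4.2.4; copying protocol Model Group 2 literally would bring back randomised treatment. Keep the pooled model as a summary, also with treatment-by-timepoint.
2. From the pooled model, add KLS-GABA minus KLS alone and KLS-GABA minus gabapentin with 95% CIs. Matched-dose KLS-GABA minus KLS from the eight-arm model is optional.
3. State whether the individual models are one model with a treatment term or separate per-arm fits. List the pooling in section 8.

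Report the added contrasts for one dependent variable, area of hyperalgesia first, as estimates without tests. State two limits: KLS-GABA minus KLS cannot separate added gabapentin from a formulation effect, and gabapentin 300 mg is not dose-matched to the 17 to 68 mg in the product.

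Cost: six extra fits (one per PD parameter) and no new data. With 5 timepoints and 6 parameters, the pooled active contrasts add 2 × 5 × 6 = 60 intervals, and the optional matched-dose ones 3 × 5 × 6 = 90. The 7 × 5 × 6 = 210 arm-minus-placebo differences are already promised by the wording. The downside is more descriptive intervals without multiplicity control.

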6.8.4. Pharmacokinetic/Pharmacodynamic Statistical Analysis

The relationship between the PK parameters and PD parameters will be investigated by estimating the Pearson and Spearman correlation coefficients by treatment. This analysis will be conducted for Part B only based on PK population.

Statistical Analysis Plan

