Subject disposition will include a summary of the number and percentage of patients entered, enrolled, and treated as well as number and percentage of patients completing the study, or discontinuing. A summary of all protocol deviations will be provided.

Demographic and baseline characteristics, medical history, concomitant medication and treatment compliance will be summarised for all subjects by treatment.

AEs will be presented in terms of the number of AEs and incidence. Standard laboratory evaluations, vital signs, physical examinations, and 12-lead ECG parameters will be summarised by treatment at each available time point.

For Part A, PK parameters estimates will be calculated by noncompartmental methods. Pharmacokinetic data will be listed for each subject, along with summary statistics. A comparison of the main PK parameters obtained (C_{max} , AUCs, t_{max} and $t_{1/2}$) after KLS-GABA and ketoprofen administration will be presented. For Part B a PK/PD correlation will be implemented for all administered doses.

In Part B, the response to ID injection of capsaicin will be assessed in 6 ways (subjective rating of pain, area and pain score of hyperalgesia, area and pain score of brush-evoked allodynia and area of flare) and summarised using descriptive statistics.

Mixed Model Repeated Measures (MMRM) will be fit to data for each PD parameter using two groups of models. Group 1 will assess longitudinal changes in Scores / Area against baseline. Group 2 will assess differences in Scores / Area between treatments for each timepoint.

LIST OF ABBREVIATIONS

Abbreviation	Definition
ADME	absorption, distribution, metabolism and excretion
AE	adverse event
AF	area of flare
ALP	alkaline phosphatase
ALT	alanine aminotransferase
API	active pharmaceutical ingredient
AST	aspartate aminotransferase
AUC _{0-12h}	area under the plasma concentration-time curve from zero to 12 hours postdose
AUC _{0-24h}	area under the plasma concentration-time curve from zero to 24 hours postdose
AUC _{0-36h}	area under the plasma concentration-time curve from zero to 36 hours postdose
AUC _{0-48h}	area under the plasma concentration-time curve from zero to 48 hours postdose
AUC _{0-t}	area under the plasma concentration-time curve from zero to the last quantifiable concentration
AUC _{0-∞}	area under the plasma concentration-time curve from zero to infinity
BMI	body mass index
BP	blood pressure
CI	confidence interval
C _{max}	maximum plasma concentration

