1.2. Study Rationale

The co-crystal KLS-GABA showed its ability to reduce mechanical allodynia, thermal hyperalgesia and oedema formation very efficiently in several preclinical studies in inflammatory and chronic pain models.

Human experimental pain models are useful in understanding the mechanisms underlying clinical pain conditions and can be used to test the analgesic efficacy of drugs used in the management of pain. Furthermore, the use of pain models excludes confounding variables due to coexisting fever, general malaise, and psychological cognitive and social aspects of illness.¹³

The capsaicin model is the most widely used model to mimic the symptoms of neurogenic hyperalgesia as observed in neuropathic pain.¹⁴

Capsaicin, an active component of hot peppers, exerts its hyperalgesic effects via transient receptor potential cation channel subfamily V member 1 receptor activation. The intradermal (ID) injection of capsaicin induces a localised release of substance P (neurokinin 1), calcitonin gene related peptide and other neuropeptides resulting in localised hyperaemia (flare), hyperalgesia, and allodynia. These effects are similar to those seen in neuropathic pain. Furthermore, ID capsaicin has been found to have a dose-dependent relationship with flare, allodynia and hyperalgesia responses in pain-free volunteers,¹⁵ and has been shown to detect the effects of a single dose of pregabalin in healthy volunteers.¹⁶ Therefore, the ID capsaicin model is a potentially useful tool to study the mechanisms of neuropathic-type symptoms and the efficacy of analgesic drugs in relieving these symptoms, such as ketamine, magnesium, lidocaine, alfentanil, diclofenac, orphenadrine, gabapentin, cannabis, lamotrigine, H1 antagonists, hydromorphone, and the lidocaine.¹⁷

According to the current literature, calcium channel α 2- δ ligands and opioids, anaesthetics, and N-methyl D-aspartate receptor antagonists seem to have an attenuating effect on capsaicin-induced hyperalgesia to mechanical stimuli. Non-steroidal anti-inflammatory drugs and other compounds showed no, or very limited, efficacy in attenuating capsaicin-induced hyperalgesia.¹⁸⁻²²

As proof of concept, the co-crystal of KLS and gabapentin could demonstrate an attenuation of secondary effects induced by a model commonly used and accepted as a paradigm of clinical neuropathic pain.

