10.5.5. Pharmacokinetic/Pharmacodynamic Statistical Analysis

Further details of the planned PK/PD correlation analysis will be provided in the SAP.

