4.2.3. Pharmacokinetic Set (Part B)

The PK Set will be defined as all subjects who received at least one dose of the IMP (KLS, KLS-GABA, gabapentin, or Placebo) and have evaluable PK data. The actual treatment received will be used for analysis. PK Set will be used for all PK analyses and endpoints.

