4.3. Treatment groups

For summary statistics, subjects will be presented in different ways, as applicable:

- for Part A:
 - by planned treatment sequence of randomized subjects ("[KLS 80 mg - GABA 34 mg] – KLS 80 mg" and "KLS 80 mg – [KLS 80 mg - GABA 34 mg]"). This presentation will be used optionally for descriptive outputs (disposition, demographics, etc.), but generally will not be used for analysis of endpoints.
 - by actual treatment of subjects in each treatment period ("KLS 80 mg - GABA 34 mg" and "KLS 80 mg"). This presentation will be used for analysis of endpoints, and optionally for descriptive outputs (disposition, demographics, etc.).
- for Part B:
 - by planned treatment of subjects ("KLS 40 mg", "KLS 80 mg", "KLS 160 mg", "KLS 40 mg - GABA 17 mg", "KLS 80 mg - GABA 34 mg", "KLS 160 mg – GABA 68 mg", "Gabapentin 300 mg", "Placebo"). This presentation will be used for descriptive outputs (disposition, demographics, etc.).
 - by actual treatment of subjects ("KLS 40 mg", "KLS 80 mg", "KLS 160 mg", "KLS 40 mg - GABA 17 mg", "KLS 80 mg - GABA 34 mg", "KLS 160 mg – GABA 68 mg", "Gabapentin 300 mg", "Placebo"). This presentation will be used for analysis of safety, efficacy and PK endpoints.

Statistical Analysis Plan

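### The PK/PD correlations are planned within single-dose arms of 16, so no estimate relates plasma level to effect across 40 to 160 mg KLS, and the PK input is not defined for Part B

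*SAP*

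**What the plan says.** Protocol 2.2.2 and SAP 1.1.4 list the relationship between plasma drug levels and pain reduction as a secondary objective of Part B. The protocol synopsis says "For Part B a PK/PD correlation will be implemented for all administered doses", and protocol 10.5.5 leaves the method to the SAP: "Further details of the planned PK/PD correlation analysis will be provided in the SAP".

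SAP 6.8.4 is two sentences. The first is "The relationship between the PK parameters and PD parameters will be investigated by estimating the Pearson and Spearman correlation coefficients by treatment". The second limits the analysis to Part B and the PK population.

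Three other places bear on the grouping:

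- SAP 4.3 lists the eight actual-treatment dose arms for Part B and adds "This presentation will be used for analysis of safety, efficacy and PK endpoints".
- SAP 6.8.3 labels its per-arm models "Individual models (by treatment"). It introduces pooling separately: "Combined models will be fit using combined treatments (i.e. different doses of the same treatment combined").
- SAP 6.8.2 states for the figures that both individual and combined groups are shown. SAP 6.8.4 does not mention combined groups.

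On the PK side, protocol 10.5.3.1 and 10.5.3.2 (derivation and analysis of PK parameters) are both headed as applying to Part A only. Protocol Appendix 2 gives three Part B blood samples: one before dosing, one just before the capsaicin injection and one 2 hours after it. PD is measured at 15, 30, 60, 90 and 120 minutes after injection (protocol 9.1). The Part B PK Set is "all subjects who received at least one dose of the IMP (KLS, KLS-GABA, gabapentin, or Placebo) and have evaluable PK data".

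**The concern.** Part B gives three doses of KLS alone and three of KLS-GABA. That dose spread is the variation in exposure that the design itself creates. A correlation computed inside one dose arm removes it and keeps only the differences between subjects in absorption and clearance at a fixed dose. It answers a legitimate question, whether concentration matters beyond dose, but it does not describe how effect changes with concentration over the range studied. Each coefficient also rests on 16 subjects.

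SAP 6.8.4 cannot be programmed as written either. It names no concentration, analyte or PD timepoint, the parameters it refers to are not planned for Part B, and its analysis set includes placebo subjects, for whom a drug-concentration correlation has no meaning. If these choices are left open, they may be made after the results are seen.

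**Working it through.** **Arm sizes.** From protocol 3.2 and 10.1: 128 subjects / 8 arms = 16 per arm. Blocks: 128 / 16 = 8, as the protocol states, with 16 / 8 = 2 subjects per arm per block. Three dose arms of one product: 3 × 16 = 48. The documents give no precision or sample size figure for the PK/PD analysis, so there is none to reproduce.

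**Dose range.** KLS: 160 / 40 = 4-fold. Gabapentin within KLS-GABA: 68 / 17 = 4-fold. The gabapentin-to-KLS ratio is constant: 17/40 = 34/80 = 68/160 = 0.425. Within any one arm the range is 1-fold.

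**Precision of one coefficient.** The 95% CI is tanh(atanh(r) ± 1.96/√(n − 3)).

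| Observed r | n = 16 | n = 48 |
|---|---|---|
| 0.1 | −0.42 to 0.57 | −0.19 to 0.37 |
| 0.2 | −0.33 to 0.63 | −0.09 to 0.46 |
| 0.3 | −0.23 to 0.69 | 0.02 to 0.54 |

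The n = 48 intervals are about 43% narrower. That is simply the effect of three times as many subjects at the same r. It shows how imprecise each by-arm coefficient is, but not the cost of discarding the dose spread.

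**Cost of discarding the dose spread.** Compare two fits on the same 48 subjects: a slope of effect on log concentration with all doses pooled, and the same slope with a separate intercept per dose. With a common slope and residual SD σ, each SE is σ/√(n × variance of log concentration used). The ratio, stratified over pooled, is therefore √[(V_between + V_within)/V_within].

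- V_between is the variance of ln(40), ln(80), ln(160) under dose-proportional exposure: (ln 2)² × 2/3 = 0.320.
- V_within = ln(1 + CV²). The CV is an assumption, shown as a range.

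| Assumed within-dose CV | V_within | SE ratio |
|---|---|---|
| 20% | 0.039 | 3.03 |
| 30% | 0.086 | 2.17 |
| 50% | 0.223 | 1.56 |
| 100% | 0.693 | 1.21 |

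For example, at CV 50%: √[(0.320 + 0.223)/0.223] = 1.56. Setting a single arm of 16 against the pooled 48 would multiply each ratio by √3, but that overstates the case, because all three arms would be reported.

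**PK input.** Set side by side, SAP 6.8.4 correlates PK parameters, the protocol derives them for Part A only, and Part B offers three concentrations. The sample before dosing precedes the only dose and carries no exposure information. That leaves two usable concentrations and five PD timepoints, with no pairing stated.

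**The case against.** The strongest reply is that this is a choice of analysis and not a defect. The objective speaks only of a possible relationship, no section promises an estimate across doses, and the synopsis wording is satisfied by one coefficient per dose. The by-dose coefficients are free of any dose effect that does not act through measured concentration; a pooled slope is not. SAP 3 plans no hypothesis testing and protocol 10.2 reports no formal sample size calculation, so no decision rule depends on this. All of that stands, and it limits the point to an optional improvement.

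The size of the gain is also open to challenge. The ratios concern regression slopes, while the plan names correlation coefficients, and they rest on assumptions that the documents do not supply. At a CV of 100% the loss is modest. That stands too.

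The table shells and the PK analysis plan are separate documents not available here and could hold more detail. Protocol 10.5.5, however, assigns the PK/PD detail to the SAP.

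A reader might infer two stronger things:

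- **That the SAP leaves the grouping undetermined.** It does use the word treatment for the pooled product once in 6.8.3. But 4.3 assigns the eight arms to efficacy and PK endpoints, 6.8.3 attaches the same phrase to the per-arm models, and the SAP says combined where it means pooling. The eight-arm reading is the natural one.
- **That the dose range goes unused altogether.** It does not: dose-response remains visible in the per-arm LS means of 6.8.3. Only a concentration-effect estimate across doses is missing.

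**Conclusion.** The point holds as a low-severity improvement. Followed as written, the SAP's only analysis of a stated secondary objective gives coefficients from 16 subjects at one fixed dose each, and none spans 40 to 160 mg KLS. Its PK input is undefined for Part B.

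Stratifying by dose costs a factor of about 1.2 to 3.0 in slope SE on the same 48 subjects. This rests on dose-proportional exposure, a common slope and residual variance across doses, and a within-dose CV between 100% and 20%. The direction of the loss does not depend on which CV in that range applies; its size does. The mismatch over PK parameters rests on the text alone and needs no assumption.

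The documents do not support reading this as a threat to the trial's validity. The analysis is exploratory, and pooling would not guarantee a clear answer: at an observed r of 0.1 or 0.2, the interval at n = 48 still includes zero.

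**What to change.** Revise SAP 6.8.4 before unblinding:

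1. State that the by-treatment correlations are per dose arm, including gabapentin 300 mg, and label them descriptive. Omit the placebo correlation.
2. Add an exploratory estimate with 95% CI of baseline-adjusted PD change on log ketoprofen concentration, starting with area of hyperalgesia (the SAP's primary endpoint). Pool the three doses within KLS alone (n = 48) and, separately, within KLS-GABA (n = 48).
3. For KLS-GABA, name the analyte for each output and state that ketoprofen and gabapentin effects cannot be separated, because the two rise together in a fixed ratio.
4. Replace the reference to PK parameters with the named Part B concentrations (before capsaicin and 2 hours after it) and the PD timepoint paired with each, for example 15 and 120 minutes. Give a rule for values below quantification on the log scale.

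The cost is SAP wording and a few extra outputs; no new samples or visits are needed. The main downside is that the pooled slope also carries any dose effect not mediated by measured concentration. Reporting the by-dose results beside it lets the reader judge that.
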